2.4.4 Exploratory Endpoints

- The proportion of subjects with confirmed disability progression/improvement at 48 weeks

The EDSS score will be summarized by visit using descriptive statistics. The proportion of subjects with confirmed disability progression or improvement at 48 weeks will be presented.

- No evidence of disease activity (NEDA)

The proportion of subjects who have no evidence of disease activity, no evidence of clinical and no evidence of MRI disease activity will be reported.

2.4.5 Analyses of Safety Data

Safety results will be summarized and presented by cohort and total in safety population.

General common rules

All safety analyses will be performed on the Safety Population as defined in Section 2.2.1, unless otherwise specified, using the following common rules:

1. For quantitative safety parameters based on central laboratory/ reading measurements, visit and cohort will use descriptive statistics to summarize results and change from baseline values. Summaries will include the value and/or the worst value of the observation period.

2. All of the values including unscheduled measurements will be assigned to the appropriate safety analysis visit window. The safety analysis visit window is defined in Section 2.5.2. In the presence of multiple measurements of the same test in the same window, the one closest to the targeted visit date will be used for the by-visit summaries.
3. The analysis of the safety variables will in general be descriptive and no systematic statistical testing is planned.

2.4.5.1 Analysis of Adverse Events

The Treatment-Emergent Adverse Events (TEAE) is defined as any AE that:

- Occurs after first dosing of study medication and through the end of the study or up through 30 days after the last dose of study treatment, or
- Is considered treatment-related regardless of the start date of the event, or
- Is present before first dosing of study medication but worsens in intensity or the investigator subsequently considers treatment related.

Dose-limiting toxicity (DLT) is defined in protocol section 5.1.1 and collected in eCRF.

Adverse event incidence tables will be presented by cohort and total, the number (n) and percentage (%) of subjects experiencing an AE. In a subset of tables, also all occurrences will be counted providing a severity of occurrence of the AE. The denominator for computation of percentages is the Safety Population within each cohort.

Not treatment emergent AE(s) summary:

- Listing of (not treatment emergent) AEs showing cohort, subject identifier, SOC, PT, verbatim term, date and day of onset, end date/time, duration, outcome, severity, date of death (if relevant), relationship to study treatment, action taken, AE seriousness and criteria.

TEAE(s) summaries:

The following TEAE summaries will be generated for the Safety Population.

Overview of TEAEs, summarizing number (%) of subjects with any

- (related/all) TEAE
- (related/all) Serious TEAE
- DLT
- (related/all) TEAE leading to death
- (related/all) TEAE of grade 3 or higher
- (related/all) TEAE leading to drug interruption
- (related/all) TEAE of special interest (AESI)
- (related/all) TEAE leading to permanent discontinuation

- TEAEs by primary SOC and PT, showing number (%) of subjects with at least one TEAE, sorted alphabetically by SOC and decreasing incidence of PTs within SOC for the total column. This sorting order will be applied to all other tables, unless otherwise specified.
- TEAEs by PT, sorted by decreasing frequency in the total column.
- All at least possibly drug related TEAEs by primary SOC and PT, showing number (%) of subjects with at least one possibly related TEAE, sorted by sorting order defined above.
- All TEAEs by maximal severity, presented by primary SOC and PT, showing number (%) of subjects with at least one TEAE by severity (ie, mild, moderate, or severe), sorted by sorting order defined above.
- Listing of TEAEs showing treatment group, subject identifier, SOC, PT, verbatim term, date and day of onset, end date/time, duration, outcome, severity, date of death (if relevant), relationship to study treatment, action taken, AE seriousness and criteria.

DLT summaries:

- DLTs by SOC and PT, showing number (%) of subjects with at least one DLT, sorted by sorting order defined above.
- Listing of DLTs showing cohort, subject identifier, SOC, PT, verbatim term, date and day of onset, end date/time, duration, outcome, severity, date of death (if relevant), relationship to study treatment, action taken, AE seriousness and criteria.

AESI summaries:

- Treatment-emergent AESI by category and PT, showing number (%) of subjects with at least one TEAE, sorted alphabetically by category and decreasing incidence of PTs within category for the total column. This sorting order will be applied to all other tables, unless otherwise specified.
- Listing of treatment-emergent AESI showing cohort, subject identifier, category, PT, verbatim term, date and day of onset, end date/time, duration, outcome, severity, date of death (if relevant), relationship to study treatment, action taken, AE seriousness and criteria.

Treatment-Emergent Suicidal Ideation and Behavior (SIB)

- Treatment-emergent SIB events will be summarized by treatment group, showing number (%) of subjects with at least one TEAE of suicidal ideation and behavior, and number (%) of subjects for each PT.
- A listing of suicidal ideations and behaviors will also be presented.
- Additional SIB analyses may be conducted as needed, such as follow-up time adjusted incidence rates of SIB event.

Serious TEAE(s) summaries:

- All serious TEAEs by primary SOC and PT, showing number (%) of subjects with at least one serious TEAE, sorted by sorting order defined above.
- All at least possibly related to ublituximab serious TEAEs by primary SOC and PT, showing number (%) of subjects with at least one possibly related serious TEAE, sorted by sorting order defined above.
- All serious TEAEs by seriousness criteria, presented by primary SOC and PT, showing number (%) of subjects with at least one serious TEAE by seriousness criteria.
- Listings of SAEs showing treatment group, subject identifier, SOC, PT, verbatim term, date and day of onset, end date/time, duration, outcome, severity, date of death (if relevant), relationship to study treatment, action taken, AE seriousness and criteria.

TEAE(s) leading to treatment discontinuation summaries:

- All TEAEs leading to treatment discontinuation, by primary SOC and PT, showing number (%) of subjects with at least one TEAE sorted by sorting order defined above.
- Listings of TEAEs leading to treatment discontinuation showing treatment group, subject identifier, SOC, PT, verbatim term, date and day of onset, end date/time, duration, outcome, severity, date of death (if relevant), relationship to study treatment, action taken, AE seriousness and criteria.

Deaths summaries:

- Number (%) of subjects who died during the study period will be presented by cohort and total.
- All TEAEs leading to death, by primary SOC and PT, showing number (%) of subjects sorted by sorting order defined above.
- Listings of deaths showing cohort, subject identifier, gender, race, age, date of death (if relevant), study day relative to first dose date, primary cause of the death

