### 9.3 ANALYSIS POPULATIONS

---

The Intent-to-Treat (ITT) population will consist of all subjects who receive at least one dose of study drug and provide some efficacy values. The primary efficacy analyses will be performed based on the ITT population.

The Safety Population will include all subjects who receive at least one dose of study drug. All safety assessments including toxicity will be performed on the Safety Population.

The modified intent-to-treat Population (mITT) will consist of all subjects who have received UTX and have one baseline and post-baseline MRI without a major protocol deviation. The criteria for a major protocol deviation will be determined and documented prior to data base lock. Subject exclusion from the mITT population will also be determined and documented prior to database lock. Supportive analyses may be performed based on the mITT population.

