### 10.5 ADVERSE EVENTS (AE'S) AND TREATMENT EMERGENT ADVERSE EVENTS (TEAE'S)

---

All AEs and SAEs occurring on study will be listed by patient. The frequency and percentages of subjects with treatment-emergent adverse events (TEAEs) will be tabulated by system organ class (SOC) and PT, where treatment-emergent is defined as any AE that:

- Occurs after first dosing of study medication and through the end of the study or up through 30 days after the last dose of study treatment, or

- Is considered treatment-related regardless of the start date of the event, or
- Is present before first dosing of study medication but worsens in intensity or the investigator subsequently considers treatment-related.

TEAEs that are considered at least possibly related to study treatment will be tabulated as well as deaths, SAEs, and events resulting in treatment discontinuation.

AEs that occur after informed consent but before first dosing of study medication will not be summarized but will be listed.

At each level of summarization, a patient will be counted only once for each AE, SOC, or PT experienced within that level. In the summation for AE severity, within each level of AE, SOC, or PT experienced, the one with the highest severity will be included. In the summation for AE's relationship to the study drug, within each level of AE, SOC, or PT experienced, the one with the closest relationship to the study drug will be included.

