1.1 Study Design and Randomization

This is a 52-week, phase IIa, placebo-controlled, multi-center study that is primarily designed to assess the optimal dosing, optimal infusion time as well as safety/tolerability of ublituximab (TG1101; UTX) in patients with RMS.

Subjects may be screened up to 4 weeks before first dosing date. Qualified subjects will receive ublituximab on Days 1, 15, and week 24. There will be at least four treatment cohorts in the study with 8 subjects (2 placebo and 6 ublituximab treatment; please see treatment schema) enrolled in each cohort.

A Data and Safety Monitoring Board (DSMB) will be established to safeguard the wellbeing of the subjects and to advise the Sponsor whether it is appropriate to expand the enrollment to a dosing cohort or to initiate next dosing cohort. Once a subject is qualified, the Site will contact the Sponsor or its designee for cohort assignment (treatment assignment). The Sponsor or its designee will issue the cohort assignment for the subject using the following procedures. If DSMB deems that a cohort is not appropriate (e.g., due to safety), enrollment to that cohort and all higher cohorts will be terminated and all future subjects will be enrolled to the lowest incomplete cohort. Upon completion of first two patients in each cohort (one on placebo and one on study drug) through 21 days, the DSMB will review safety data and assuming no safety concern is raised, the remaining qualified subjects will be enrolled into such cohort.

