2.1 Analysis Variables

Baseline for both efficacy and safety variables are defined as the last non-missing value on or before the first dose of Ublituximab.

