- Concomitant medications (extension) are those taken at any time between last study treatment and end of extension.

Technical details related to calculating dates, imputation for missing dates, etc. are described in Section [2.5](#).

[2.1.2 Study Treatment Exposure](#)

Treatment exposure for ublituximab/placebo is summarized with following variables:

- The total number of infusions of placebo
- The total number of infusions of ublituximab received over the 3 expected infusions.
- The overall number of infusions of ublituximab, number and percentage (based on all infusions) of infusions completed with/without interruption and infusions not completed.
- The number and percentage of patients (based on all patients with at least one infusion) with and without any infusion complication (interruption or stop).
- The percentage of planned total infusion received.

[2.1.3 Efficacy Variables](#)

[2.1.3.1 Primary Efficacy Variable](#)

The primary efficacy variable will be responder rate at week 4 (2 weeks after W3D15, the second scheduled infusion of ublituximab), where responders are subjects who have reduced B-cell depletion by $\geq 95\%$.

[2.1.3.2 Secondary Efficacy Variables](#)

The secondary efficacy variables are as follows:

- Number of new Gd-enhancing lesions at 24 and 48 weeks
- Number of new or enlarging T2 lesions at 24 and 48 weeks
- Annualized relapse rate (ARR)
- Relapse rate reduction (RRR)
- Percent of relapse free subjects

- Reduction in B cells (CD19+), memory (CD19+CD27+) and naïve (CD19+CD27-) B cells at baseline, day 1 (pre dose) and 2; week 2; Day15 (pre-dose); week 4 and every 4 weeks thereafter until the next infusion at week 24 (pre-dose and 2 days post-dose) 25, 28, 36, 40, 44 and 48
- To examine sustained B cell reduction during the first and third infusions
- Additional immune profiling (CD4+, CD8+, IL10 and NK cells) at baseline, day 1 (pre dose) and 2; week 2, Day 15 (pre-dose); week 4 and every 4 weeks thereafter until the next infusion at week 24 (pre-dose and 2 days post dose) 25, 28, 36, 40, 44 and 48
- PK (ADME) profile of ublituximab at day 1 (pre-dose); week 2; day 15 (pre-dose); weeks 4, 24 (pre-dose) and 25

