2.2 Analysis Populations

2.2.1 Safety Population

The Safety Population will include all subjects who receive at least one dose of Ublituximab. All safety assessments for Ublituximab including toxicity will be performed on the Safety Population.

The Placebo Safety Population will include all subjects who receive at least one dose of Placebo. All safety assessments for Placebo including toxicity will be performed on the Placebo Safety Population.

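### The SAP creates a Placebo Safety Population but adapts neither the TEAE rule nor the safety baseline to it, so some placebo-period events can count as ublituximab TEAEs

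*SAP*

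**What the plan says.** **Populations.** Protocol 9.3 has a single safety set: "The Safety Population will include all subjects who receive at least one dose of study drug". SAP 2.2.1 replaces it with two sets, one for subjects with any ublituximab dose and one for subjects with any placebo dose. Of the second it says: "All safety assessments for Placebo including toxicity will be performed on the Placebo Safety Population".

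**Crossover.** Each cohort has 2 placebo and 6 ublituximab subjects. Placebo is infused on Days 1 and 15. Ublituximab then starts on Day 28 (Protocol 5.2) or once Day 28 is complete (footnote b to the dosing table), and the assessment schedule restarts.

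**TEAE rule.** SAP 2.4.5.1 uses the limbs of Protocol 10.5. The first is that the event "Occurs after first dosing of study medication and through the end of the study or up through 30 days after the last dose". The second takes in any event considered related, whatever its start date. The third, in the protocol's wording, takes in an event that "Is present before first dosing of study medication but worsens in intensity or the investigator subsequently considers treatment-related". SAP 2.5.1.2 treats a missing relationship as related.

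**Where the rule is applied.** SAP 2.4.5 states: "All safety analyses will be performed on the Safety Population as defined in Section 2.2.1, unless otherwise specified". SAP 2.4.5.1 ties the TEAE tables and their denominators to that ublituximab-defined set.

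**Baseline.** SAP 2.1 gives one: "Baseline for both efficacy and safety variables are defined as the last non-missing value on or before the first dose of Ublituximab".

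**Terminology.** *Study medication* is not defined. SAP 1.1 sets placebo against study drug ("Upon completion of first two patients in each cohort (one on placebo and one on study drug) through 21 days"), whereas SAP 2.1.2, headed as study treatment exposure, covers both ("Treatment exposure for ublituximab/placebo is summarized with following variables").

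**The concern.** Once safety is split by drug and the same subjects sit in both sets, each event and each measurement has to be assigned to a period. The SAP does not do this. The TEAE wording predates the split, and the baseline serves ublituximab only.

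Two things are at stake. First, the ublituximab TEAE tables can contain events that began before any ublituximab was given. That sits badly with Protocol 10.1, which asks for safety to be presented by the ublituximab dose actually received. Second, the placebo period is the only concurrent control for infusion and premedication effects: infusion times match within cohort (Table 1), and Protocol 6.2.1.2 gives the same premedication before placebo. Infusion time is part of a primary objective, yet under the stated rules part of the placebo safety data cannot be summarised at all.

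**Working it through.** The plan states no figure on this point, so there is none to reproduce. The check sets the rules side by side and then does arithmetic on the schedule.

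**1. Which placebo-period events reach the ublituximab TEAE tables?**

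| Event starting in the placebo period | Study medication = ublituximab only | Study medication includes placebo |
|---|---|---|
| Judged not related, no later worsening | Out (non-treatment-emergent listing) | In, first limb |
| Judged at least possibly related | In, second limb | In |
| Relationship missing | In, second limb with SAP 2.5.1.2 | In |
| Worsens after the first ublituximab infusion | In, and properly so | In |

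The second and third rows are wrong for a ublituximab table on either reading. The first row is wrong only on the broader reading.

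**2. Size in the ublituximab tables**

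- Subjects exposed to the problem: 2/8 = 25% per cohort, which is 12/48 with six full cohorts or 8/32 with the four-cohort minimum.
- One placebo starter whose only event of a given term fell in the placebo period adds 1/8 = 12.5 points to the cohort row, and 1/48 = 2.1 to 1/32 = 3.1 points to the total column.
- Ublituximab time per subject is 48 × 7 = 336 days; placebo time is 28 days. The pooled placebo share is 12×28 / (12×28 + 48×336) = 336/16,464 = 2.0%. With four cohorts it is 8×28 / (8×28 + 32×336), also 2.0%.
- The expected rise in a cohort row is (2/8) × q × (1 − p). Here p is the ublituximab-period risk of the term and q is the risk of a placebo-period event that enters the table. The documents give neither. Assuming each lies between 0.1 and 0.5, the rise runs from 0.25 × 0.1 × 0.5 = 1.25 points to 0.25 × 0.5 × 0.9 = 11.25 points. On the ublituximab-only reading q covers only related or unassessed events, so the lower end is the more realistic.

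**3. Baseline**

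After the first placebo dose the laboratory schedule has 4 visits: Days 2, 8 and 15, and Week 4. With ublituximab starting on Day 29 (no Day 0), these are Days −27, −21, −14 and −1 on the ublituximab clock. With a Day 28 start, the first three are Days −26, −20 and −13, and the Week 4 sample is the Day 1 pre-dose value, which is itself the baseline. So 0 of 4 placebo visits are post-baseline, against 16 of 16 scheduled visits after the first ublituximab dose.

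Three consequences follow:

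- A placebo-period change from baseline would run backwards in time.
- The laboratory and ECG shift tables to the worst post-baseline value contain no placebo value.
- The laboratory by-visit summaries, which SAP 2.4.5.2 limits to post-baseline visits, contain none either.

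**4. Which first dose?**

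SAP 2.5.1.2 (AE date imputation) and 2.5.2 (relative days) refer to the first dose without naming the drug. In SAP 2.5.3, W3 is the second ublituximab infusion. Anchored on the first placebo dose, W3 is Day 42 or 43, so the Week 4 window would run from Day 49 or 50 to Day 42 and be empty. Only the ublituximab anchor works, and with it all placebo visits before crossover fall ahead of the first window (Day 1). The imputation rule has no such internal check.

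**The case against.** The strongest reply is that study medication means ublituximab, so the first limb already cuts at the first ublituximab infusion. Much supports this. The SAP replaces study drug with ublituximab in its Safety and ITT definitions, and it ties baseline, ARR and the W3 and W24 windows to ublituximab. A reader might infer from the undefined term that every placebo-period event enters the ublituximab tables; the documents do not establish that. The reply leaves the second limb untouched, however. That route may be narrow, since Protocol 10.7.1 frames causality around ublituximab and no frequency is given, but it is a written rule. The worsening limb is most naturally read as worsening after that dose, and no error is claimed there.

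A reader might also infer that a placebo AE table would be mostly ublituximab time: 336 of 364 days (92%) to end of study, or 17 to 18 of 45 days (38–40%) if follow-up stops 30 days after the Day 15 placebo dose. SAP 2.4.5 to 2.4.5.5 list no such table, and for a subject who crosses over and completes treatment, the last dose of study treatment is the Week 24 ublituximab infusion. Those figures describe an output that is not planned.

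Nor is all placebo-period safety lost. The post-baseline restriction is written for laboratory visits only. Vital signs are summarised at all scheduled visits and ECG interpretation by visit and time point, and listings retain the data. Protocol section 9 also says the SAP will include table shells; none are in the available text, so a placebo output cannot be excluded. Even so, a shell could not supply a baseline that the SAP does not define.

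**Conclusion.** The point holds in a limited form. SAP 2.2.1 assigns placebo safety to a new population, but the TEAE rule was not adapted. On the likelier reading of study medication, related or unassessed placebo-period events still enter the ublituximab TEAE tables; on the broader reading all of them do. Separately, with only a pre-ublituximab baseline, placebo-period change-from-baseline and shift results and laboratory by-visit summaries cannot be produced. Vital-sign and ECG by-visit summaries are not restricted in that way.

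The effect is visible in a cohort row of 8 and small in the total column. Safety analyses are descriptive, so no error rate is involved. The primary endpoint is unaffected: efficacy uses nominal visits (SAP 2.5.2), and Week 4 is tied to the second ublituximab infusion (SAP 2.1.3.1). The sizes assume full cohorts of 8, crossover on Day 28 or 29 and 48 weeks of ublituximab follow-up. Severity: minor to should-fix.

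**What to change.** 1. Define a ublituximab TEAE as onset, or worsening of an existing event, on or after the first ublituximab infusion. State that, for the ublituximab tables, *study medication* in SAP 2.4.5.1 and *first dose* in SAP 2.5.1.2 and 2.5.2 mean that infusion.
2. Define a placebo TEAE as onset or worsening from the first placebo infusion to just before the first ublituximab infusion. Add a pre-placebo baseline for laboratory, vital-sign and ECG data, use nominal placebo visits, and specify one placebo-period safety table. Add the Placebo Safety Population to the population counts in SAP 2.3, which omit it.
3. For the ublituximab tables, remove from the relatedness and missing-relationship limbs any event that began in the placebo period and did not worsen afterwards. Keep the missing-equals-related default for every event that begins or worsens on ublituximab, so that this conservative rule is not weakened.

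The cost is a few lines of SAP text and one or two tables from data already scheduled. The placebo table will be imprecise: with no events, the exact upper 95% limit is 1 − 0.025^(1/12) = 26.5% for 0/12 and 1 − 0.025^(1/8) = 36.9% for 0/8.

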### 5.1.2 DETERMINATION OF DOSE-LIMITING TOXICITY

---

The patient population used for determination of DLT will consist of subjects who have met the minimum safety evaluation requirements of the study, and/or who have experienced a DLT. Minimum safety requirements will be met if, during the first 4 weeks of treatment of the study, the patient completes all required safety evaluations, and is observed for at least 4 weeks following the first dose of ublituximab. Subjects who experience a DLT will be considered evaluable regardless of the number of doses received.

Subjects who discontinue treatment early due to disease progression or withdrawal will be asked to have all end-of-treatment safety evaluations performed as described in the protocol. If a patient withdraws from treatment during the first 4 weeks due to any reason other than a DLT, that patient may be replaced.

---

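### The SAP takes DLT percentages over everyone dosed with ublituximab rather than the protocol's DLT-evaluable subjects, so any treated subject who is non-evaluable without a DLT lowers the reported proportion

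*SAP*

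**What the plan says.** Protocol section 5.1.2 gives DLTs their own population: "The patient population used for determination of DLT will consist of subjects who have met the minimum safety evaluation requirements of the study", and/or who had a DLT. To meet the minimum, a subject must complete all required safety evaluations in the first four weeks and must be someone who "is observed for at least 4 weeks following the first dose of ublituximab". A subject with a DLT counts as evaluable however few doses were given. A subject who withdraws from treatment in that period for another reason can be replaced.

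The SAP takes over the event definition but not the population. Section 2.4.5.1 states: "Dose-limiting toxicity (DLT) is defined in protocol section 5.1.1 and collected in eCRF". It does not cite 5.1.2. Section 2.2 defines Safety, Placebo Safety, ITT, mITT and PK populations, and no DLT-evaluable set. Section 2.4.5 sets the default: "All safety analyses will be performed on the Safety Population as defined in Section 2.2.1, unless otherwise specified". Section 2.2.1 says who that is: "The Safety Population will include all subjects who receive at least one dose of Ublituximab". No minimum observation time is attached.

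Section 2.4.5.1 then puts a DLT row in the TEAE overview for the Safety Population and orders a separate table: "DLTs by SOC and PT, showing number (%) of subjects with at least one DLT". No other denominator is given for either. The rule for adverse-event tables is "The denominator for computation of percentages is the Safety Population within each cohort".

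**The concern.** The two documents use different denominators for the same quantity. A subject who receives ublituximab, is lost before four weeks or misses required evaluations, and has no DLT, is outside the protocol's DLT population because the observation is incomplete. In the SAP tables the same subject counts as someone observed without a DLT. If that subject is replaced, both people sit in the SAP denominator, although only the replacement, once evaluable, belongs in the protocol's.

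Finding the optimal dose and infusion time is a primary objective, and SAP section 2.1.4 names DLTs first among the inputs to the safety analysis. With 6 subjects on ublituximab per cohort, one extra person in the denominator visibly moves a percentage, and it can only move it down.

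**Working it through.** The documents give no DLT rate, DLT threshold or DLT-based sample size, so there is no figure of the plan's to reproduce. The check is direct.

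**Inputs**
- x: subjects with a DLT. This is the same under both rules, because protocol 5.1.2 makes every such subject evaluable and the Safety Population includes everyone dosed.
- E: DLT-evaluable subjects in the cohort. The base is 6 on ublituximab (protocol section 5.1, Table 6; SAP section 1.1).
- w: subjects given ublituximab who are non-evaluable and had no DLT. The documents give no rate; 0, 1 and 2 per cohort are assumed.

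**Formulas**
- Protocol proportion = x / E
- SAP proportion = x / (E + w)
- Ratio of SAP to protocol = E / (E + w), which never exceeds 1 and equals 1 only when w = 0

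**Results for x = 1**

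| Base | w | Replaced? | Protocol | SAP | Ratio |
|---|---|---|---|---|---|
| 6 | 0 | – | 1/6 = 16.7% | 1/6 = 16.7% | 1.000 |
| 6 | 1 | yes | 1/6 = 16.7% | 1/7 = 14.3% | 0.857 |
| 6 | 2 | yes | 1/6 = 16.7% | 1/8 = 12.5% | 0.750 |
| 6 | 1 | no | 1/5 = 20.0% | 1/6 = 16.7% | 0.833 |
| 6 | 2 | no | 1/4 = 25.0% | 1/6 = 16.7% | 0.667 |
| 8 | 1 | yes | 1/8 = 12.5% | 1/9 = 11.1% | 0.889 |
| 8 | 2 | yes | 1/8 = 12.5% | 1/10 = 10.0% | 0.800 |

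The base of 8 assumes that the two placebo subjects who cross over to ublituximab after Day 28 are pooled with their parent cohort. The ratio does not depend on x: with 2 DLTs and one replaced subject, 2/6 = 33.3% becomes 2/7 = 28.6%, again 0.857.

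**Precision.** Exact 95% intervals are 0.4–64.1% for 1/6, 0.4–57.9% for 1/7 and 0.3–52.7% for 1/8.

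**Who counts in w.** Withdrawal from treatment alone is not enough. Protocol 3.3 requires AE follow-up for 30 calendar days after the last dose, which is longer than four weeks (28 days) after the first, and 5.1.2 asks early discontinuers to have the end-of-treatment safety evaluations. A subject who stops treatment but completes the required evaluations and observation can remain evaluable. A placebo subject who leaves before any ublituximab is outside the SAP Safety Population and adds nothing to w.

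**The case against.** The strongest reply is that the protocol itself supports the SAP. Section 7.2 treats all subjects as evaluable for toxicity from first treatment on Day 1, and section 9.3 places safety assessments, toxicity included, on the Safety Population. Section 5.1.2 belongs to the treatment plan, so it could be an operational rule for cohort decisions and replacement, with 9.3 governing the final tables. This stands in part: the protocol never says how the three sections relate. But 7.2 and 9.3 speak of toxicity in general, while 5.1.2 is specific to DLTs, and nothing in the general statements cancels it. If 9.3 is meant to govern, the SAP should say so.

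It is also fair that the shift is small beside the intervals, that every DLT is listed by cohort and subject so the count is visible, and that the size rests on an assumed number of non-evaluable subjects.

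Three stronger readings are tempting and not supported. A reader might infer that replacements dilute the proportion too. They do not: a replacement who completes the four weeks, or has a DLT, is in both denominators, and replacement slightly eases the relative dilution (6/7 = 0.857 against 5/6 = 0.833). A reader might infer that the reported figure is always too low; with w = 0 it is identical. A reader might also infer that cohort progression is distorted. The documents state no numeric DLT threshold and no DLT rate for the DSMB to review, and protocol 5.1.3 rests progression on the total safety data.

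**Conclusion.** The point holds as a mismatch between protocol 5.1.2 and SAP sections 2.2 and 2.4.5.1. Followed as written, the SAP gives a DLT percentage equal to or below the protocol-defined one, and strictly below it whenever a cohort has at least one DLT and at least one treated subject who is non-evaluable without a DLT. For 6 evaluable subjects, 1 DLT and one or two replaced non-evaluable subjects, the reported figure is 14.3% or 12.5% instead of 16.7%. This rests on the assumed one or two such subjects and on reading 5.1.2 as the specific rule for DLTs.

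The consequence is confined to reported percentages. The DLT count is unaffected, and nothing in the documents shows that a decision rule changes or that the DLT percentage is the leading tolerability measure. It is a modest point, worth settling because it costs little.

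**What to change.** - Add a DLT-evaluable population to SAP section 2.2 using the definition in protocol 5.1.2, and cite 5.1.2 beside 5.1.1 in section 2.4.5.1. State which scheduled assessments count as required, so that the flag can be derived.
- Use it as the denominator for the DLT row of the TEAE overview and for the DLT table by SOC and PT. Keep the Safety Population for all other adverse-event tables.
- List treated subjects who are not DLT-evaluable, by cohort, with the reason and whether they were replaced.
- State whether crossover subjects are counted with their parent cohort in the DLT tables.
- State how 5.1.2 relates to protocol 7.2 and 9.3.
- Reconcile the replacement wording: for early withdrawals without a DLT, protocol 3.3 says they *will* be replaced and 5.1.2 says they *may* be.

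Exact confidence intervals for the DLT proportions are optional, since the safety analysis is descriptive. The cost is SAP wording, one population flag and one listing, plus a clarification of the protocol text. No new data are needed.
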